10.13 Baseline Characteristics

Baseline data including, but not limited to demographics, clinical characteristics, and angiographic characteristics will be summarized using descriptive statistics.

10.14 Pooling Across Centers

Analyses will be presented using data pooled across centers. Key baseline and study endpoint variables will be presented by study site to assess any potential site effects.

10.15 Final Report

A final report will be completed, even if the study is prematurely terminated. At the conclusion of the trial, a multi-center abstract reporting the results will be prepared and may be presented at a major meeting(s). A multi-center publication may also be prepared for publication in a reputable scientific journal. The publication of results from any single center experience within the trial is not allowed until the aggregate study results have been published, unless there is written consent from the Sponsor. Data may also be used for submissions to regulatory agencies as part of post-market clinical follow-up.

11. Core Lab

11.1 Imaging Core Lab

The Imaging Core Lab is composed of independent medical doctor(s) who are not participants in the study. The Core Lab is responsible for assisting in the development of specific criteria used for the categorization of clinical endpoints in the study. A

web-based electronic database will be provided for Core Lab to review and adjudicate images. Additional details related to the Core Lab are specified in the Core Lab Charter.

The independent imaging core lab will review images from the Immediate Post Procedure and Final Follow-Up to assess at minimum occlusion grading. An imaging core lab charter will provide procedure for core lab review. Penumbra is responsible for tracking images received and basic quality review.

12. Study Administration

12.1 Clinical Trial Termination/Withdrawal

Subjects may be terminated or withdrawn from the study for the following reasons:

- Voluntary withdrawal of consent— meaning that a subject voluntarily chooses not to participate further in the study. All data collected up to the withdrawal of consent will be maintained in the study database. Withdrawn subjects will not have any additional follow-up and will not be replaced.
- Lost to follow-up— a subject will be considered lost-to-follow-up when contact is not achieved at the last required follow-up visit window. At a minimum, the effort to obtain follow-up information will include three (3) attempts to make contact via telephone or e-mail. These efforts to obtain follow-up will be recorded in the subject's study files.
- Subjects may also be withdrawn at the Investigator's discretion if within their best interest. A subject's participation in the clinical study will be terminated if the Investigator believes that this is in the subject's best medical interest or if the subject no longer complies with the clinical study requirements

The sponsor may temporarily suspend or prematurely terminate the study at any time for the following reasons:

- Suspicion of risk to subjects
- If no positive IRB/EC decision is obtained or if the judgement of the IRB/EC is revoked
- If the applicable regulatory body has made an irrevocable objection
- If it transpires that continuation of study cannot serve any scientific purpose, and this is confirmed by the IRB/EC
- Business reasons

The Sponsor will document reasons for study suspension or premature termination and notify the PIs. The Sponsor will ensure that the IRB/ECs and regulatory authorities are notified in a timely manner.

The Sponsor will continue to provide resources to fulfil the obligations from the study protocol and existing agreements for following up the subjects enrolled in the study.

The Principal Investigators will promptly inform the enrolled subjects at his/her site, if appropriate.

If the Sponsor temporarily suspends the study and wishes to resume it, the Sponsor will inform the PIs, IRB/ECs, and (if appropriate) regulatory authorities. The Sponsor will provide a rationale for resuming the study. IRB/ECs must provide written approval before the study is resumed.

12.2 Missing Visits

Every effort should be made to bring subject in to scheduled follow-up visits. Any study subject who does not attend a scheduled follow-up visit should be contacted by site personnel to reschedule. If the missed visit was due to a reportable adverse event, an AE CRF must be completed.

12.3 Protocol Adherence and Amendments

Prior to beginning the study, the Principal Investigator must sign the protocol signature page documenting his/her agreement to conduct the study in accordance with this protocol. Deviations outlined in section 7.6.4 from the protocol must be documented and reported to Penumbra as soon as possible, and to the IRB/EC per local guidelines and government regulations.

16.1 Acronyms and Abbreviations

Acronyms	Definition
ADE	Adverse Device Effect
AE	Adverse Event
BPC	Bare-Platinum Coils
CRF	Case Report Form
CTA	Computed Tomography Angiography
DSA	Digital Subtraction Angiography
EC	Ethics Committee
EDC	Electronic Data Capture
FDA	Food and Drug Administration
GCP	Good Clinical Practices
IA	Intracranial Aneurysms
ICH	Intracranial Hemorrhage
ID	Identifier
IRB	Institutional Review Board
ISO	International Organization for Standardization
IV	Intravenous
LAR	Legally Authorized Representative
mRS	modified Rankin Scale
NIHSS	National Institute of Health Stroke Scale
SAE	Serious Adverse Event
SAH	Subarachnoid Hemorrhage
UADE	Unanticipated Adverse Device Effect

16.2 Modified Rankin Scale

0	No Symptoms at all
1	No significant disability, despite symptoms; able to perform all usual duties and activities
2	Slight disability; unable to perform all previous activities but able to look after own affairs without assistance
3	Moderate disability; requires some help, but able to walk without assistance
4	Moderately severe disability; unable to walk without assistance and unable to attend to own bodily needs without assistance
5	Severe disability; bedridden; incontinent, and requires constant nursing care and attention
6	Death

16.3 Hunt and Hess Grading Scale

Grade	Clinical Features
I	No symptoms or minimal headache and slight nuchal rigidity
II	Moderate to severe headache, nuchal rigidity, and no neurologic deficit other than cranial nerve palsy
III	Drowsiness, confusion, or mild focal neurologic deficit
IV	Stupor, moderate to severe hemiparesis, possible decerebrate rigidity, and vegetative disturbances
V	Deep coma, decerebrate rigidity, and moribund appearance

16.4 Definitions

16.4.1 Stroke

An acute episode of focal or global neurological dysfunction due to brain or retinal infarction, or from any intracranial hemorrhage inclusive of subarachnoid, intraventricular or intraparenchymal hemorrhages with signs and symptoms that persist for 24 hours or more. The 24-hour criterion is excluded if the patient undergoes cerebrovascular surgery or dies during the first 24 hours.

16.4.2 Major Ipsilateral Stroke

Major ipsilateral stroke is an acute episode of focal or global neurological dysfunction due to brain or retinal infarction, or from any intracranial hemorrhage (ICH) inclusive of subarachnoid, intraventricular or intraparenchymal hemorrhages in the same hemisphere of the target aneurysm and which is associated with an increase of 4 or more points on the NIHSS at 24 hours after stroke onset.

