5.1 Inclusion Criteria

1. Patient age \geq 18 years
2. Patient having embolization of intracranial aneurysms
3. WAVE Extra Soft Coil is the final finishing coil
4. Penumbra SMART COIL System accounts for at least 75% of total number of coils implanted
5. Informed consent obtained per IRB/EC requirements

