8.5 Handling of Multiplicity

There will be no adjustment for multiplicity in SURF study reporting.

9 Subgroup Analysis

The following subgroup analyses will be performed for all primary and secondary effectiveness and safety endpoints using the ITT population:

- **Adjunctive technology used during treatment:** Balloon, Stent, Other, None
- **Age at time of informed consent (years):** < 65, \geq 65
- **Sex:** Female, Male
- **Ethnicity:** Hispanic or Latino, Not Hispanic or Latino
- **Race:** American Indian or Alaska Native, Asian, Black or African American, White, Other
- **Site country:** North America (US/Canada), Europe
- **Target aneurysm location:** Extradural ICA, ICA, ACA, MCA, Posterior Circulation, Other
- **Target aneurysm size:** Small (\leq 5 mm at its largest diameter), Medium (6 to 14 mm at its largest diameter), Large (15 to 24 mm at its largest diameter), Giant (\geq 25 mm at its largest diameter)
- **Target aneurysm status:** Ruptured, Unruptured
- **Target aneurysm anatomical location:** Bifurcation, Sidewall, Other
- **Neck width:** Small-Neck (< 4 mm Neck Width), Wide-Neck (\geq 4 mm Neck Width or Dome-to-Neck Ratio (defined as the maximum of dome width, depth, and height divided by neck width) $<$ 2)
- **Target aneurysm previously treated:** Previous Treatment at Admission, No Previous Treatment at Admission

Descriptive statistics and two-sided 95% Wald confidence intervals will be presented for each subgroup.

10 Safety Analysis

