10.2 Secondary Safety Analysis

For the secondary safety endpoints, frequency counts, percentages, and two-sided 95% Wald confidence intervals will be reported using the ITT population:

- **Major ipsilateral stroke:** The percentage of patients who experience major ipsilateral stroke adverse event(s), as defined in the SURF study protocol.
- **Device related SAE at final follow-up:** The percentage of patients who experience serious adverse event(s) with probable or definite relationships to the SMART Coil System from the date of procedure (day 0) through the final follow-up visit at 1 Year \pm 90 Days from the date of procedure.
- **All-cause morbidity and mortality:** The percentage of patients who experience either of the following events:
 - **All-cause morbidity:** mRS 3 to 5 at the final follow-up evaluation or worsening of mRS by 2+ points the date of procedure (day 0) through the final follow-up visit at 1 Year \pm 90 Days from the date of procedure. If the final follow-up mRS is missing, mRS as assessed at the 7-day and/or discharge visit will be substituted.
 - **All-cause mortality:** Death for any reason from the date of procedure (day 0) through calendar day 365

Adverse events occurring after the final follow-up visit at 1 Year \pm 90 Days and deaths occurring after day 365 will be separately tabulated and not included in endpoint and adverse event rates.

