10.3 Analysis of Adverse Events

In the SURF study, only device-related or procedure-related adverse events and serious adverse events (SAEs) will be collected from procedure through discharge. After discharge, only neurological SAEs will be collected. Additional information for Symptomatic Intracranial Hemorrhage and Ischemic Stroke will be collected on Event of Interest case report forms.

Frequency counts and percentages will be provided for all reportable adverse events and broken down as well based on relationships to the device and procedure. Reportable adverse event data will be listed for each patient, including the type of event/verbatim term, start date, seriousness, action taken, outcome, and causality (if appropriate). The onset of adverse events will also be shown relative (in number of days) to the date of procedure.

The specific categories analyzed will be those that are reported by at least three (3) percent of the patients. As there is no CEC for this study, all adverse events will be reported based on the assessment from the clinical study sites.

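### The major ipsilateral stroke definition requires a 24-hour NIHSS score and has no rule for death before then, so read literally it leaves out strokes fatal within 24 hours of onset.

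*Combined protocol and SAP*

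**What the plan says.** Major ipsilateral stroke is a secondary safety endpoint (protocol 4.2.2). Protocol 16.4.2 sets two conditions beyond the occurrence of an infarct or intracranial hemorrhage. The lesion must lie "in the same hemisphere of the target aneurysm", and the stroke must be "associated with an increase of 4 or more points on the NIHSS at 24 hours after stroke onset".

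The general stroke definition in 16.4.1 also has a 24-hour element, namely persistence of signs and symptoms, and it provides for early death: "The 24-hour criterion is excluded if the patient undergoes cerebrovascular surgery or dies during the first 24 hours". Section 16.4.2 has no such sentence.

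SAP 10.2 defines the endpoint as "The percentage of patients who experience major ipsilateral stroke adverse event(s), as defined in the SURF study protocol". It is reported in the ITT population as a count, a percentage and a 95% Wald interval. On who classifies events, SAP 10.3 states: "As there is no CEC for this study, all adverse events will be reported based on the assessment from the clinical study sites". Protocol 7.6.2 adds medical monitor review of events that bear on the safety endpoints.

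**The concern.** The severity test depends on a measurement that can be taken only in patients alive 24 hours after onset. A patient whose ipsilateral stroke is fatal sooner cannot have that score. If the definition is applied as worded, that patient stays in the ITT denominator and contributes nothing to the numerator, although the outcome is worse than in any survivor who meets the 4-point threshold.

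The rate of major stroke would then be too low, and the missing events would all be fatal. Someone who uses the major-stroke line to judge the neurological safety of the coil system would not see from that line that such events had been left out.

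**Working it through.** The documents state no expected rate, precision or sample size for major ipsilateral stroke, so there is no planned figure to reproduce. The check is of the text first, then of the possible size.

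**1. Does any text supply the missing rule?**

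- *16.4.1.* The early-death exception waives persistence of symptoms. It does not mention NIHSS. Section 16.4.2 restates the stroke definition in full instead of referring back to it, so the exception does not clearly carry over. Even if it did, it would not supply a score.
- *SAP 10.2.* It refers back to the protocol. The same section gives a substitution rule for a missing final mRS in the morbidity endpoint, but none for a missing NIHSS.
- *SAP 12.* The imputation analyses cover the primary effectiveness and primary safety endpoints only.
- *Elsewhere.* Nothing assigns an NIHSS value to death.

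Applied literally, a stroke fatal before 24 hours fails a necessary condition and is not counted.

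**2. How many patients might this affect?**

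Inputs: 2 deaths in 496 patients within 24 hours of intervention (protocol Section 1, interim results of the earlier registry), and a planned enrolment of 800 (protocol 10.2).

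- Scaled count: 2/496 × 800 = 3.2.
- Exact (Clopper-Pearson) 95% CI for 2/496: 0.049% to 1.449%. Multiplied by 800, this is 0.4 to 11.6 patients.

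This is only a rough guide. The deaths are from all causes, and the registry included arteriovenous malformations, fistulae and other lesions. The clock also starts at the intervention, not at stroke onset. The number of ipsilateral strokes among these deaths could be zero. On the other side, a stroke that starts later in follow-up and is fatal within 24 hours of onset lies outside this figure.

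**3. What would a few patients do to the rate?**

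The counted strokes below are assumptions (1%, 2% and 3% of 800), because the documents give no rate. Three omitted fatal strokes are added to each. Intervals are p ± 1.96 × √(p(1 − p)/800).

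| Counted strokes | Rate (95% CI) | With 3 added | Rate (95% CI) |
|---|---|---|---|
| 8 | 1.0% (0.3 to 1.7) | 11 | 1.4% (0.6 to 2.2) |
| 16 | 2.0% (1.0 to 3.0) | 19 | 2.4% (1.3 to 3.4) |
| 24 | 3.0% (1.8 to 4.2) | 27 | 3.4% (2.1 to 4.6) |

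The shift is 3/800 = 0.375 percentage points each time. That is smaller than the interval half-widths before the addition (0.69, 0.97 and 1.18 points), but it is not trivial against a rate of 1%.

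**4. Two related gaps in the same definition**

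- *Reference score.* Section 16.4.3 measures the NIHSS rise in symptomatic hemorrhage against baseline. Section 16.4.2 names no reference. NIHSS is not listed in protocol 6.6 to 6.9 or in Table 2. Those lists of data are open-ended, and the Event of Interest forms may collect it, but the documents do not say so.
- *Side.* Eligibility requires only "Patient having embolization of intracranial aneurysms", with no restriction on location. The SAP Section 9 location categories, "Extradural ICA, ICA, ACA, MCA, Posterior Circulation, Other", do not record side. No rule says how the hemisphere condition applies to a target aneurysm that has no side.

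**The case against.** The strongest reply is that nothing states that these strokes are excluded. A site could reasonably treat a fatal stroke as meeting a 4-point threshold, and the medical monitor reviews such events. The deaths are not lost to the study either. All deaths are reported, they enter all-cause mortality through day 365 and the Kaplan-Meier estimate, and a stroke SAE that starts on day 0 or day 1 counts in a primary safety endpoint. The study is descriptive, and this endpoint has no test or threshold.

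Most of that stands, and it confines the problem to one secondary rate. It does not remove it. Counting the fatal case requires a departure from the wording, each site would decide for itself, and the monitor has no written rule to apply. All-cause mortality does not report major stroke.

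A reader might infer more than the documents support, in four ways.

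- *A percentage undercount.* This would treat every early registry death as an ipsilateral stroke and set it against a stroke rate that has no source in the documents.
- *Strokes from midline targets are excluded.* The hemisphere condition is undefined for them, so sites may classify them either way. No direction of bias follows.
- *A count of targets without a side.* One cited series of 33 aneurysms gives an anterior-circulation share of 85%. That does not separate sided from midline aneurysms, and the documents give no midline share.
- *16.4.1 and 16.4.2 contradict each other.* The waiver in 16.4.1 concerns duration of symptoms, not severity. Its absence from 16.4.2 leaves a gap, not an inconsistency.

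**Conclusion.** The concern holds for strokes fatal within 24 hours of onset. On a literal reading of 16.4.2, as adopted by SAP 10.2, they are non-events, and the major ipsilateral stroke rate is biased low for the most severe cases. The conclusion rests on that literal reading; a site that scores death as meeting the threshold would avoid the bias, but nothing tells it to.

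The number affected is unknown and is plausibly between none and a few of 800, judged from an all-cause figure that fits the question poorly. Severe strokes in patients who survive to a 24-hour assessment are not affected by this gap. The primary endpoints, all-cause mortality and the sample size are also unaffected. The missing reference score and the undefined side are matters of consistency between sites, secondary to the main point.

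**What to change.** Add one sentence to protocol 16.4.2 and repeat it in SAP 10.2: *An ipsilateral stroke that is fatal before the 24-hour NIHSS can be obtained counts as a major ipsilateral stroke.*

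In the same revision:

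- name the reference score for the NIHSS increase in 16.4.2, as 16.4.3 already does for symptomatic hemorrhage;
- state how ipsilateral is decided when the target aneurysm has no side, and leave the hemisphere rule as it is for targets that have one.

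The sentence should cover death only. Extending it to early cerebrovascular surgery would make a stroke major whatever its severity, which changes the endpoint and does not just close the gap.

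The cost is wording in two documents, agreed before database lock so that fatal events are not classified after the data are known. No visit, scheduled assessment or sample-size change is needed. The downside for the sponsor is that the reported rate may rise.

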16.4.3 Intracranial Hemorrhage

Bleeding in the cranium of the brain inclusive of subarachnoid, intraventricular or intraparenchymal hemorrhages, symptomatic or asymptomatic. A symptomatic intracranial hemorrhage is associated with a 4 or more points increase on the NIHSS from baseline.

16.4.4 Morbidity

Defined as mRS 3 to 5 or worsening of mRS from baseline by 2 points

16.4.5 Perforation

The piercing or rupturing of a blood vessel; perforations can be detected or observed angiographically.

16.4.6 Dissection

Angiographic evidence of a tear in the arterial wall as defined by the occurrence of intramural hematoma.

16.4.7 Vasospasm

Spasm of a blood vessel, resulting in prolonged decrease in lumen diameter. Symptomatic vasospasm is defined as the development of new focal neurological signs, deterioration in level of consciousness, or both, when the cause was felt to be ischemia attributable to vasospasm after other possible causes of worsening (for example, hydrocephalus, seizures, metabolic derangement, infection, or oversedation) had been excluded.

16.4.8 Recanalization

Defined as an increase in size of the remnant in contrast filling of the aneurysm sac using results of immediate post-stent/embolization angiography as baseline.

16.4.9 Aneurysm Size

Aneurysm size should be reported in millimeters in 3 dimensions as well as categorical taxonomy:

- Small Neck: < 4 mm
- Wide Neck: ≥ 4 mm or a dome to neck ratio of less than 2 mm
- Small Aneurysms: ≤ 5 mm at its largest diameter
- Medium Aneurysms: 6 – 14 mm at its largest diameter
- Large Aneurysms: 15 mm – 24 mm at its largest diameter
- Giant Aneurysms: ≥ 25 mm at its largest diameter

[figure not shown]

[figure not shown]
Figure 2. Aneurysm Sizing

16.4.10 Angiographic Outcome

The primary effectiveness endpoint is occlusion of the treated aneurysms. This is defined as the proportion of aneurysms with Class 1 and 2 occlusion as described by Roy et al (*Stroke 2001;32:1998-2004*):

- Class 1 – Complete occlusion
- Class 2 – Residual neck
- Class 3 – Residual aneurysm

Figure 3: Classification of Angiographic Results

Adopted from Roy, Milot and Raymond. Stroke 2001;32:1998-2004

STATISTICAL ANALYSIS PLAN

**SURF: A Prospective, Multicenter Study Assessing the Embolization of
Intracranial Aneurysms using WAVE™ Extra Soft coils, a part of the
Penumbra SMART COIL® System**

Protocol CLP 13669

Version 3.0

Contents

1	Overview	3
2	Sample Size	3
3	Interim Analysis	4
4	Analysis Populations	4
4.1	Definitions	4
5	Statistical Methods	4
6	Baseline Characteristics	5
7	Patient Disposition	5
8	Effectiveness Analysis	5
8.1	Primary Effectiveness Analysis	5
8.2	Secondary Effectiveness Analysis	6
8.3	Imaging Outcomes Analysis	7
8.4	Economic Analysis	7
8.5	Handling of Multiplicity	8
9	Subgroup Analysis	8
10	Safety Analysis	9
10.1	Primary Safety Analysis	9
10.2	Secondary Safety Analysis	9
10.3	Analysis of Adverse Events	10
10.4	Analysis of Deaths	10
11	Pooling Across Centers	10
12	Missing Data and Imputation Methods	11
13	Changes to Planned Analyses	11
14	References	12
15	Revision History	12

1 Overview

SURF is a postmarket, real-world, prospective, multicenter single-arm study. Its objective is to demonstrate the safety and efficacy of the Penumbra SMART COIL® System, including the WAVE™ Extra Soft Coils (WAVE) as a fill and finish coil, in the treatment of intracranial aneurysms. An independent core lab will read images to assess aneurysm occlusion rates, facilitating an analysis on the sensitivity and specificity of MRA imaging to detect residual aneurysm blood flow at final follow-up as compared to DSA (Section 8.3 of this document).

Approximately 800 patients will enroll at up to 60 global sites. Each site will be limited to a maximum enrollment of 120 patients (15% of total enrollment). An estimated 10% of enrolled patients will experience attrition by final follow-up.

This Statistical Analysis Plan (SAP) elaborates on statistical methods outlined in the study protocol and presents analysis conventions. The SAP will be signed off prior to database lock.

2 Sample Size

Approximately 800 patients will enroll in this post-market study, resulting in 720 patients who achieve final follow-up after 10% anticipated attrition. This sample size provides adequate precision to estimate the primary effectiveness and safety endpoints.

Primary Endpoint	Assumption for Observed Rate ^[1]	95% CI ^[2]	Precision
Adequate occlusion defined as Raymond-Roy Occlusion Class I and II at final follow-up	89% (320/360)	86% to 92%	Greater than $\pm 3.5\%$
	89% (401/450)	86% to 92%	Greater than $\pm 3\%$
	89% (481/540)	86% to 92%	Greater than $\pm 3\%$
	89% (561/630)	87% to 91%	Greater than $\pm 3\%$
	89% (641/720)	87% to 91%	Greater than $\pm 3\%$
Device-related SAE up to 7 days or discharge	2.8% (11/400)	1.1% to 4.4%	Greater than $\pm 2\%$
	2.8% (14/500)	1.4% to 4.2%	Greater than $\pm 1.5\%$
	2.8% (17/600)	1.5% to 4.2%	Greater than $\pm 1.5\%$
	2.9% (20/700)	1.6% to 4.1%	Greater than $\pm 1.5\%$
	2.8% (22/800)	1.6% to 3.9%	Greater than $\pm 1.5\%$
SAEs within 24 hours post-procedure	9.0% (36/400)	6.2% to 11.8%	Greater than $\pm 3\%$
	9.0% (45/500)	6.5% to 11.5%	Greater than $\pm 2.5\%$
	8.8% (53/600)	6.6% to 11.1%	Greater than $\pm 2.5\%$
	8.9% (62/700)	6.8% to 11.0%	Greater than $\pm 2.5\%$
	8.9% (71/800)	6.9% to 10.9%	Greater than $\pm 2.5\%$

^[1] Set at SMART CLP 10023 Registry interim observed results (data on file at sponsor)

^[2] Two-sided 95% Wald normal approximation binomial proportion confidence interval

3 Interim Analysis

As there will be no interim analyses for the purpose of terminating the study early for success or futility, alpha adjustments will not be made to the confidence intervals in the final analysis. However, interim analysis may be performed for the purpose of publication or regulatory submission of SURF results.

4 Analysis Populations

